**PROSPECTIVE, MULTICENTRIC, BEFORE AFTER STUDY TO  
EVALUATE THE EFFECTIVENESS AND THE SAFETY OF A MEDICAL  
DEVICE IN THE TREATMENT OF COMMON WARTS AND PLANTAR  
WARTS**

Clinical investigation plan #:	23E2007
NCT number:	NCT06214559
Date and version :	V1.0 of 27.10.2023
Title of the clinical investigation:	PROSPECTIVE MULTICENTRIC, BEFORE AFTER STUDY TO EVALUATE THE EFFECTIVENESS AND THE SAFETY OF A MEDICAL DEVICE IN THE TREATMENT OF COMMON WARTS AND PLANTAR WARTS
Sponsor:	PODERM Professional Swiss Footcare Laboratories [name] SWITZERLAND
Development phase:	Exploratory study Interventional MD without CE mark
Objectives:	
Primary objective: To evaluate the effectiveness of Sérum VERRUPRO® in the treatment of warts, assess by the evolution of the wart diameter after 35 days of treatment.
 
Secondary objectives:
 
 
- To evaluate the effectiveness of Sérum VERRUPRO® in the treatment of warts, assessed by the investigator , after 35 days of treatment.
 
- To evaluate the effectiveness of Sérum VERRUPRO® in the treatment of warts assess by the investigator clinical examination, after 35 days of treatment.
 
- To illustrate the effectiveness of Sérum VERRUPRO® on the skin aspect before and after the treatment assess by photographs.
 
- To evaluate the patient's opinion of Sérum VERRUPRO® on the effectiveness, tolerance, and acceptability after 35 days of treatment.
 
- To evaluate the safety and tolerance of Sérum VERRUPRO®
 

Design:	Prospective, multi center, before/after study.
Planned Sample Size:	33 included patients to expect result on 30 patients. 60% of patients will be treated for a wart on their back of hands or fingers. 40% of patients will be treated for a plantar wart.
Number of investigational study sites:	2 sites in Tunisia
Inclusion criteria:	
 
1. Patient having given freely her/his informed, written consent.
 
2. Patient having a good general health.
 

	
 
3. Age: more than 18 years.
 
4. Patient cooperative and aware of the device's modalities of use and the necessity and duration of the controls so that perfect adhesion to the protocol can be expected.
 
5. Patient being psychologically able to understand information and to give his/her consent.
 
6. Patient presenting at least 1 common wart, present since less than 6 months, on the fingers, back of the hands (60% of patients) and/or at least 1 plantar wart (40% of patients).
 
7. Patient presenting wart of a size between 0,1 and 0,5 cm.
 
8. Women of childbearing potential should use an accepted contraceptive regimen (at the Investigator's discretion) since at least 12 weeks before the beginning of the study and during all the study.
 

Exclusion criteria:	
 
1. For plantar wart: wart on the point of support.
 
2. Wart with keratosis.
 
3. Wart in mosaic.
 
4. Pregnant or nursing woman or planning a pregnancy during the investigation.
 
5. Patient considered by the investigator likely to be non-compliant with the protocol.
 
6. Patient enrolled in another clinical trial during the test period.
 
7. Patient having a known allergy or hypersensitivity to one of the constituents of the tested products.
 
8. Patient with a condition or receiving a medication which, in the investigator's judgment, put the patient at undue risk.
 
9. Patient suffering from serious or progressive diseases (to investigator's discretion) such as uncontrolled diabetes, peripheral circulatory disease, immunocompromised patient HIV, psoriasis, lichen planus, immunosuppressive pathology, chronic venous insufficiency, Peripheral Arterial Obstructive Disease, delay or lack of unguel growth ...
 
10. Patient with cutaneous pathology on studied zone other than warts.
 

Investigational device:	
Name	Sérum VERRUPRO®
Galenic form	Liquid solution in bottle with a brush applicator
Dosage	Twice daily
Duration	35 days
Administration route	Topical application
Endpoints:	
Primary endpoint  Clinical examination performed by the investigator to evaluate the diameter of the wart at D0 and 35 days after treatment.  The effect of the product on clinical parameters will be evaluated by comparing the mean diameter before and after treatment.
 
Secondary endpoints:
 
 
- The global improvement of the wart will be assessed by the investigator after 35 days of treatment.
 
- Clinical examination performed by the investigator to evaluate the roughness, thickness and the number of dermal papillae of the wart at D0 and 35 days after treatment.  The effect of the product on these clinical parameters will be evaluated by a comparison before and after treatment.
 
- Illustration of the effectiveness of Sérum VERRUPRO® on the skin aspect before and after the treatment with photographs.
 

	
 
- Analysis of the answers to the patient questionnaire regarding effectiveness, tolerance, and acceptability of the investigational device 35 days after treatment.
 
- Products safety will be assessed by collection of Adverse Events (AEs) throughout the study. AEs will be summarized and tabulated by severity, causality, action taken and outcome, using descriptive statistics.
 
- Product tolerance will be assessed by the investigator at D0 (before the product use) and D35 by a clinical examination.
 

Study Procedures:	
Visit 1: informed consent, medical interview, collection of medical history and previous treatment, checking of the inclusion and exclusion criteria, patient inclusion, selection of the studied wart, clinical examination of the wart by the investigator, tolerance parameter evaluation, preparation of the wart by the investigator (removal of the stratum corneum if needed), photography of the selected wart, application of the product by the patient, distribution of daily log and product.
 
Visit 2: clinical examination by the investigator, tolerance parameter evaluation, photography of the selected wart, assessment of the global improvement by the investigator, patient subjective questionnaire, product tolerance evaluation, record of AE, concomitant treatments, study end.

Statistical methods:	
The following analysis populations will be studied and will be considered for the statistical analysis:
 
 
- Safety population: any patient having used the investigational device.
 
- ITT (Intent-to-Treat): any patient included in the study with at least a post-basal value.
 
- PP population: any patient included having used at least once the investigational device and without any major deviation to the CIP.
 
 
Descriptive analysis: Quantitative data will be summarized using adapted statistics (number of values, number of missing values, mean, standard deviation, minimum and maximum values) by time point. Categorical data will be summarized in frequency (N) and percentage (%).
 
Primary endpoint: To evaluate the effectiveness of Sérum VERRUPRO® in the treatment of warts, assessed by the evolution of the wart diameter after 35 days of treatment. Clinical examination will evaluate the diameter of the wart at D0 and 35 days after treatment. The effect of the product on clinical parameters will be evaluated by comparing the mean before and after treatment.
 
A paired t-test will be carried out on the change from baseline outcome (D35-D0) to assess whether the mean value of the diameter of the wart decrease significantly from baseline.
 
Secondary endpoints:
 
 
- Global improvement Clinical examination of roughness, thickness and number of dermal papillae.
 
- Subjective evaluation by the patient.
 

	
 
- Tolerance by the investigator
 
 
Each secondary endpoints listed above, will be summarized using adapted statistics.
 
Safety assessment by collecting all the AEs occurred during the study will be summarized in frequency and percentage for the Safety population.
 
Each statistical analysis test will be two tailed with a type I error set at <math>\alpha=0.05</math>.
 
Statistical software : SAS v9.4

Foreseen study duration:	
Clinical investigation beginning: Q4 2023
 
Clinical investigation end: Q2 2024
 
Clinical investigation global duration: 4 months
 
Duration by patient: 35 days

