#### FLOW-CHART

Procedure	Visit 1 Day 0	Visit 2 Day 35
Days	D0	D35±7
Informed consent form signature	●	
Medical interview, medical history, previous and concomitant medications collection by the investigator	●	
Checking of the inclusion and exclusion criteria	●	
Patient inclusion	●	
Selection of the studied wart	●	
Clinical examination (diameter, roughness, thickness, dermal papillae) by the investigator	●*	●
Preparation of the selected wart (removal of the stratum corneum if needed) by the investigator	●	
Clinical examination for evaluation of product tolerance by the investigator	●*	●
Photograph of the selected wart	●* (after removal of the stratum corneum)	●
Treatment application by the patient	● (under investigator control at the site on D0 then at home)	
Patient subjective evaluation questionnaire		●
Global improvement evaluation by the investigator		●
Distribution of daily log and products	●	
AE and concomitant treatment collection	●	●
Study end		●

\*Before treatment application

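### Where the stratum corneum is removed at D0, the before and after photographs show the wart in different surface states, and the D0 picture does not show the wart as it was examined

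*Combined protocol and SAP*

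**What the plan says.** The synopsis gives photographs their own line among the secondary objectives, "To illustrate the effectiveness of Sérum VERRUPRO® on the skin aspect before and after the treatment assess by photographs", and under Endpoints it repeats the line as a secondary endpoint: "Illustration of the effectiveness of Sérum VERRUPRO® on the skin aspect before and after the treatment with photographs".

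The order of steps at D0 appears in two places, and they agree. Under Study Procedures, Visit 1 lists the clinical examination of the wart, then the tolerance evaluation, then "preparation of the wart by the investigator (removal of the stratum corneum if needed), photography of the selected wart". In the Flow-chart, the D0 cell of the photograph row carries the note "after removal of the stratum corneum".

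Preparation has its own row in the Flow-chart, "Preparation of the selected wart (removal of the stratum corneum if needed) by the investigator", marked at Day 0 only. Visit 2 runs "clinical examination by the investigator, tolerance parameter evaluation, photography of the selected wart, assessment of the global improvement by the investigator", with no preparation step.

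Under Statistical methods, the secondary endpoints to be summarised are global improvement, the clinical signs, the patient's evaluation and tolerance, followed by "Each secondary endpoints listed above, will be summarized using adapted statistics". Photographs are not in that list. The text does not say how they are to be read or which pairs will be shown.

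**The concern.** A before/after pair can be interpreted only if the two pictures differ in treatment and elapsed time and in nothing else that alters the look of the lesion. Here a physical intervention on the wart surface falls immediately before the first picture and has no counterpart at the second. The endpoint is skin aspect, which is what such an intervention changes.

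The study has no comparator, so no control pair shows what preparation alone does to the appearance. The D0 photograph would also be the natural visual check on the D0 diameter, roughness and thickness. If it is taken in a different state from the one examined, it cannot serve that purpose.

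**Working it through.** The plan gives no figure for the photograph endpoint, so there is none to reproduce. The check is a comparison of the steps listed under Study Procedures and in the Flow-chart.

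**Step 1. State of the wart at each observation, in a patient whose stratum corneum is removed**

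| Observation | D0 | D35 |
|---|---|---|
| Examination (diameter, roughness, thickness, papillae) | Listed before preparation: unprepared | No preparation listed: not freshly prepared |
| Photograph | After preparation: freshly prepared | No preparation listed: not freshly prepared |

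The D0 photograph is the only one of the four observations made on a freshly prepared surface. It therefore matches neither the D35 photograph nor the D0 examination. In a patient who needs no removal, all four observations share one state and the problem does not arise.

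**Step 2. How firm the reading is**

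- The D0 photograph following preparation is explicit in the Flow-chart note and agrees with the Visit 1 sequence, so it is the planned order and not a slip in one place.
- The D0 examination preceding preparation rests on the order of listing, which is the same in Study Procedures and the Flow-chart. The Flow-chart footnote says only that the examination and the photograph both come before the product is applied. It does not place the examination relative to preparation.

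**Step 3. How many pairs are affected**

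The synopsis plans "33 included patients to expect result on 30 patients", so about 30 complete pairs can be expected. The share *f* of warts needing removal is not given. Affected pairs = 30 × *f*:

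| Assumed *f* | Affected pairs of 30 |
|---|---|
| 0% | 30 × 0 = 0 |
| 25% | 30 × 0.25 = 7.5 |
| 50% | 30 × 0.50 = 15 |
| 75% | 30 × 0.75 = 22.5 |
| 100% | 30 × 1 = 30 |

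The plan does not narrow this range. It also lists no record of which patients had removal, so as written the affected pairs might not be identifiable afterwards.

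**Step 4. Direction**

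The documents do not describe how removal changes the wart's appearance. A pared wart may look flatter at D0, which would hide improvement, or rawer, which would exaggerate it. The documents do not decide between the two.

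**The case against.** The strongest reply is that this touches nothing on which the study's conclusion rests. The study is labelled exploratory. The photographs carry no test and no type I error, and the word 'illustrate' can be taken to mark them as descriptive. The primary comparison uses the investigator's diameter, whatever the moment of the picture. The Flow-chart openly states the condition of the wart in the D0 photograph. Warts with keratosis are excluded, which may leave few that need removal. All of this stands, and it is why the point is minor. It does not make the pairs comparable where removal is done.

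A reader might infer three stronger things, none of which the documents support.

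- *Every pair is mismatched, in the device's favour.* Removal is conditional, and the direction is unknown (steps 3 and 4).
- *The sponsor will show only flattering pairs.* The objective is worded as if the effect were already established, and no display rule is given. But a photograph is scheduled for every patient at both visits, and nothing says that a subset will be chosen. Showing all pairs fits the text equally well. The text available is also a synopsis and flow-chart, so the absence of a rule means only that none is stated there.
- *Selection alone could produce impressive shrinkage.* In a simulation of 30 normally distributed changes with zero mean, the best 3 average 1.67 SD. The plan gives no SD. At assumed SDs of 0.05, 0.10 and 0.15 cm this is 1.67 × 0.05 = 0.08, 1.67 × 0.10 = 0.17 and 1.67 × 0.15 = 0.25 cm. The calculation assumes three displayed pairs chosen on outcome, which the plan does not state. It ignores the floor at zero: a 0.1 cm wart, the smallest eligible, cannot shrink by 0.17 cm. It also models diameter, whereas the endpoint is skin aspect. It does not measure a defect in this plan.

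**Conclusion.** The concern holds in a limited form. Followed as written, the plan gives before/after photographs that are not like for like in every patient whose stratum corneum is removed. In those patients the D0 picture also fails to show the wart as examined. The number affected lies between 0 and 30 of about 30 pairs, and the direction is unknown.

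The mismatch between the two photographs rests on the stated position of the D0 photograph and on the absence of any preparation at Visit 2. The mismatch between the D0 photograph and the D0 examination rests on taking the order of listing at Visit 1 as the order of conduct.

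The order of the photographs does not affect the primary paired t-test. Whether removal itself contributes to the measured change in diameter is a separate question and does not depend on when the picture is taken. Severity is minor: a stated secondary endpoint is hard to interpret, and the remedy is cheap.

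**What to change.** - Take a D0 photograph before preparation, with a scale in frame, and use it as the 'before' member of each pair. Put a scale in the D35 picture too.
- If a picture after preparation is still wanted, keep it, label it as such, and do not pair it with D35.
- Record for each patient whether the stratum corneum was removed.
- Amend the Visit 1 sequence and the Flow-chart photograph row to match, and state there that the clinical examination precedes preparation, if that is the intention.

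The cost is one additional photograph per patient at D0, one item on the case report form and a small change of wording. Treatment, visits, sample size and the primary analysis stay as they are.

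As minor reporting advice only: present the pairs of all patients in the report, and word the objective neutrally, for example as documenting the skin aspect. This lengthens the report appendix.

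### The plan never asks whether the study wart was growing, stable or shrinking before D0, although D0 is the only control for the primary endpoint

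*Combined protocol and SAP*

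**What the plan says.** The Design row of the synopsis describes a "Prospective, multi center, before/after study". No concurrent group appears anywhere, and the Statistical methods row specifies one two-sided paired t-test at 0.05 on the D35-D0 change in diameter. The Endpoints row states how that change will be read: "The effect of the product on clinical parameters will be evaluated by comparing the mean diameter before and after treatment".

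Entry of the wart is governed by these provisions:

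- Criterion 6, common warts: "Patient presenting at least 1 common wart, present since less than 6 months, on the fingers, back of the hands". This is an upper age limit with no lower one.
- Criterion 6, plantar warts: "and/or at least 1 plantar wart (40% of patients". No age limit is attached to this clause.
- Criterion 7: "Patient presenting wart of a size between 0,1 and 0,5 cm".
- Exclusion criteria on the wart itself: location ("For plantar wart: wart on the point of support"), keratosis and mosaic form.

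The Study Procedures row places everything before treatment in one visit: "checking of the inclusion and exclusion criteria, patient inclusion, selection of the studied wart, clinical examination of the wart by the investigator". The Flow-chart agrees, with all of these steps on Day 0. Medical history and previous treatment are collected at that visit, but no criterion uses them to judge whether the wart is changing.

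**The concern.** In a before/after study each patient's D0 value stands in for the untreated outcome at D35. That works only if the wart would have stayed about the same size without treatment. Here nothing requires this, nothing checks it and nothing records it. There is no run-in and no measurement before D0, so the wart's course before entry cannot be recovered afterwards except by late recall.

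The avoidable part is narrow but real. If a patient says at Visit 1 that the wart has been shrinking for weeks, the plan as written still allows that wart to be selected, and its further regression goes into the primary endpoint as product effect. A wart still enlarging at entry does the reverse and can mask an effect. Either way the primary result cannot be interpreted without knowing the prior course.

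A smaller matter is the wording of criterion 6. The 6-month phrase sits in the common-wart clause only. If it was meant for both types, the two sites could apply it differently to the roughly 40% of patients with plantar warts.

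**Working it through.** **What the plan gives.** 30 evaluable patients out of 33 included (Planned Sample Size); eligible diameter 0.1-0.5 cm, that is 1-5 mm (criterion 7); paired t-test, two-sided 0.05 (Statistical methods). It states no effect size, SD of change, power or untreated clearance rate, so it has no figure of its own on this point to reproduce.

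**Is a changing wart kept out?** Taking the wart-related provisions in turn: criterion 6 concerns type, site and, for common warts, age; criterion 7 concerns size; the exclusions concern location, keratosis and mosaic form. None concerns recent course. Eligibility check, selection and baseline examination all fall on D0, so no earlier measurement exists. The answer is no.

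**How large a change makes the test significant?** With n = 30 there are 29 degrees of freedom and the critical t is 2.045. The observed mean decrease must reach 2.045/√30 = 0.373 SD of the change.

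**Illustration with an inactive product.** All of the following are assumptions:

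- baseline diameter uniform on 1-5 mm, mean 3 mm;
- a fraction q of warts clear untreated by D35, so their change is minus their baseline;
- the other warts change by g on average, with SD 0.5 mm.

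Expected mean change = -3q + (1 - q)g. For q = 10%:

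- g = 0: -3(0.10) + 0 = -0.30 mm
- g = 0.2 mm: -0.30 + 0.90 × 0.2 = -0.12 mm

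The changes are strongly skewed, so the chance of significance was simulated (20,000 trials per setting, n = 30). Each cell gives the expected mean change and the share of trials significant for a decrease:

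| q | other warts unchanged | others grow 0.1 mm | others grow 0.2 mm |
|---|---|---|---|
| 5% | -0.15 mm; 7% | -0.055 mm; 1.2% | +0.04 mm; 0.1-0.2% |
| 10% | -0.30 mm; 23% | -0.21 mm; 8.3% | -0.12 mm; 2.6% |
| 20% | -0.60 mm; 67% | -0.52 mm; 46% | -0.44 mm; 29% |

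With q = 0 and no growth the share is about 2.5%, the nominal one-sided level. With noise SD 1.0 mm and no growth, the shares at q = 5, 10 and 20% are about 8%, 18% and 51%. Independent repeats agree to within about one percentage point.

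**Reading the table.** Modest untreated clearance can produce a significant decrease with an inactive product, and modest growth in the remaining warts can cancel it. The documents supply neither q nor g. Wart age does not enter the calculation, so the table shows the exposure created by having no concurrent control. It does not measure the effect of criterion 6.

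**The case against.** The strongest reply is that the root limitation is the uncontrolled design, which the sponsor states openly in a study labelled exploratory. Perfect eligibility wording would still leave regression that begins after D0 in the endpoint. This stands, and it limits what any eligibility change can achieve. It does not excuse admitting warts already reported as regressing, because the primary objective is still effectiveness, judged by a significance test.

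Several stronger readings are tempting and are not supported:

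- *The bias always favours the product.* A reader might infer this, and it is true of a shrinking wart. But no rule excludes a growing wart either, and a very recent wart may still be enlarging. The table shows that growth of 0.2 mm brings the 10% clearance case back to about the nominal level.
- *Criterion 6 selects the warts most likely to regress.* That would require recent warts to clear more often within 35 days than older ones. Nothing in the documents says so.
- *A common-versus-plantar difference would be confounded with lesion age.* The plan pools the two types in a single test and schedules no such comparison.
- *The 6-month limit should be extended to plantar warts.* The missing limit may be loose drafting of one sentence. The documents give no basis for a new limit, only for clarifying the existing one.

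It can also be objected that recall over a few weeks is unreliable for lesions of 1-5 mm, and that a table by wart age in about 30 patients cannot separate natural regression from product effect. Both are fair. They are reasons to treat the added data as descriptive, but not reasons to leave them uncollected.

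**Conclusion.** The point holds in a limited form. The plan neither screens for nor records the study wart's course before D0, while D0 is the sole comparator and the change from it is attributed to the product. Warts already regressing count toward the product and warts still growing count against it; the net direction and size cannot be determined from the documents.

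The size is illustrative only. At 10% untreated clearance, with 30 patients, an inactive product, baseline uniform on 1-5 mm and noise SD 0.5 mm, the chance of a significant decrease runs from about 23% (other warts unchanged) to about 3% (others growing 0.2 mm on average). The clearance rate, the growth, the noise and the baseline distribution are all assumed. The spread between these figures is the finding; neither is an estimate of this trial's false-positive rate. The point justifies a cheap improvement at entry, but does not show that the result will be biased in a particular direction.

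**What to change.** 1. At the existing D0 medical interview, record for the study wart the approximate onset date and whether the patient reports that it grew, stayed the same or shrank over the previous 4 weeks.
2. Add to the selection step at Visit 1 that a wart reported as already shrinking over that period is not chosen as the study wart.
3. Tabulate the D35-D0 change in diameter by reported prior course and by wart age, labelled descriptive, with no test.
4. State in criterion 6 whether the 6-month limit is meant to cover plantar warts. No new limit is proposed here.

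The cost is two interview questions, one selection rule, one table and one clarified sentence, plus a few screen failures. Recall is imprecise, so the bias is reduced and not removed. Regression that starts after D0 remains in the endpoint because there is no concurrent control, and the report should say so.

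### The listed eligibility criteria set no washout and no limit on other treatment of the study wart, so the before/after change can include its effect

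*Combined protocol and SAP*

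**What the plan says.** **Design and analysis.** The Design row describes a "Prospective, multi center, before/after study". There is one product and no comparator. The primary analysis is a two-sided paired t-test at 0.05 on the D35-D0 change in wart diameter. Statistical methods attributes that change to the product: "The effect of the product on clinical parameters will be evaluated by comparing the mean before and after treatment".

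**Eligibility.** Two exclusion criteria come near the point. No. 6 is "Patient enrolled in another clinical trial during the test period". No. 8 is "Patient with a condition or receiving a medication which, in the investigator's judgment, put the patient at undue risk". Inclusion 4 and exclusion 5 concern adherence to the protocol. Exclusion 10 concerns skin disease other than warts.

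**Recording.** Visit 1 includes "collection of medical history and previous treatment" and Visit 2 includes "record of AE, concomitant treatments, study end". The Flow-chart also has concomitant treatment collected at both visits.

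**Populations.** ITT is "any patient included in the study with at least a post-basal value". PP is "any patient included having used at least once the investigational device and without any major deviation to the CIP". Statistical methods lists Safety, ITT and PP, but does not say which of them the primary t-test uses.

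**The concern.** In a controlled trial, other wart treatment would be expected in both arms and would largely cancel. Here nothing cancels it. If a patient is still responding at D0 to an earlier treatment, or is using another one alongside the product, the resulting shrinkage falls between D0 and D35 and is read as the product's effect.

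The criteria shown do not prevent this. A patient who treats the wart with another remedy outside any trial, and is not at undue risk from it, meets every listed criterion. The compliance criteria do not help, because the text shown states no restriction to comply with. The treatment records would identify some of these patients, but no rule shown uses them for eligibility, for deviations or in the analysis. A choice made after the data are seen would be post hoc.

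At stake is the reading of the single primary test, which at n = 30 can be moved by a few large changes.

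**Working it through.** **Comparison of the criteria with the gap.**

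| Criterion | What it controls | Other treatment of the study wart? |
|---|---|---|
| Inclusion 4, exclusion 5 | Adherence | Only if a restriction exists; none is shown |
| Inclusion 6 | Site of the wart; age of a common wart (under 6 months) | No |
| Exclusion 6 | Concurrent trial | Only treatment given in another trial |
| Exclusion 8 | Undue risk to the patient | Only if unsafe |
| Exclusion 10 | Other skin disease at the site | No |

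The remaining criteria (consent, health, age, size, contraception, pregnancy, wart type, allergy, systemic disease) do not bear on it.

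**Size.** The plan has no figure of its own to reproduce here. It gives 33 included for 30 with results, but no expected change, SD or power, and nothing on how many patients use other treatment.

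*Inputs from the plan:* n = 30, two-sided alpha 0.05, wart size 0.1 to 0.5 cm (1 to 5 mm).

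*Inputs assumed:* baseline diameter uniform on 1 to 5 mm (mean 3 mm), inert product, zero mean change without other treatment, and SD of that change 0.5, 1.0 or 1.5 mm. A cleared wart has diameter 0 at D35.

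*Threshold.* The test is significant when |mean change| / (SD/√30) exceeds t(0.975; 29 df) = 2.045. The mean decrease must therefore exceed 2.045/√30 = 0.373 SD.

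*Spurious mean change.* This is (number affected × shrinkage) / 30. Two cleared warts give 2 × 3/30 = 0.20 mm on average. Three warts shrunk by 1 mm give 3 × 1/30 = 0.10 mm. Large changes in a few patients also inflate the SD, so the rejection rate was simulated (40,000 trials per cell). Ranges cover the three SDs, with and without a floor of zero on diameter.

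| Other treatment, inert product | Chance of a significant decrease |
|---|---|
| None | about 2-2.5% (nominal 2.5%) |
| 1 wart cleared | 3-5% |
| 2 cleared | 6-8% |
| 3 cleared | about 10-15% |
| 6 cleared | 33-79% |
| 3 shrunk by 0.5 mm | 3-7% |
| 3 shrunk by 1 mm | 4-11% |
| 6 shrunk by 1 mm | 7-34% |

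If measurement noise is also added to cleared warts, the figure for 2 cleared falls to 5-7%.

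**Opposite direction.** Assume a true change of -0.6 mm, SD 1.0 mm, and previously treated warts that do not respond. With 3 such warts the mean is -0.6 × 27/30 = -0.54 mm and power is 81%. With 6 it is -0.6 × 24/30 = -0.48 mm and power is 70%. With none, power is 89%.

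**Background change.** Assume instead a mean spontaneous change of -0.2 mm, inert product and diameters floored at zero. The chance of a significant decrease is then about 56%, 18% and 8% at SD 0.5, 1.0 and 1.5 mm with no other treatment at all. With one wart cleared by another treatment it is about 60%, 25% and 13%.

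**The case against.** **The study is exploratory, and the 2.5% benchmark is artificial.** Spontaneous change enters D35-D0 too, as may the D0 removal of stratum corneum, which Study Procedures lists after the clinical examination. The background scenario shows that a small drift can outweigh the whole effect of a few treated warts. This stands. A reader might infer that an eligibility line would bring the false-positive risk back to 2.5%. It would not; it limits one avoidable contributor among several.

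**The size rests on assumptions.** This stands. The largest figures need 6 of 30 study warts cleared by another treatment, and the mildest scenario (0.5 mm in 3 warts) barely moves the result.

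**The text reads as a synopsis with a flow-chart.** It refers to the CIP for deviations, and a fuller CIP may restrict other treatment or class it as a major deviation. This also stands, and it applies to the central claim as much as to the PP set. The documents therefore do not support the statement that the trial has no such rule, only that none is shown.

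**There are partial safeguards.** Treatment history is taken before the study wart is selected, and a patient may have several warts, so an investigator could choose an untreated one. Nothing shown requires it. PP could drop affected patients, but nothing shown makes other treatment a major deviation.

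**Conclusion.** The omission is real in the criteria as listed, and a correction is worthwhile. Followed as written, they admit patients whose study wart is under other treatment, and the analysis credits their whole change to the product. Confidence is medium because a fuller CIP may exist.

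The size cannot be known from the documents. Given the assumed baseline distribution and SDs, an inert product and no background change, two cleared warts in 30 take the chance of a significant decrease to about two to three times its nominal 2.5%. Any spontaneous change comes on top of that.

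Three stronger readings are not supported:

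- *That the bias must favour the product.* Resistant warts could reverse it, and a treatment that finished acting before D0 adds nothing to D35-D0.
- *That the plan commits the primary test to ITT, so that affected patients are certain to be in it.* Statistical methods assigns no population to that test.
- *That a washout criterion would remove the problem.* Treatment started after D0 remains possible, and the screen is only as good as the patient's history and the length of the washout.

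**What to change.** 1. Add an exclusion criterion: wart-directed treatment of the study wart that is ongoing at D0, or was given within a washout period before D0 whose length the sponsor sets. Check it from the history already taken at Visit 1. If a fuller CIP already has such a rule, bring it into the listed criteria.
2. At both visits, record whether each reported treatment was applied to the study wart.
3. State which population the primary paired t-test uses. Whichever it is, pre-specify one sensitivity analysis without patients who had other treatment of the study wart between D0 and D35. Report it beside the main result, with a note that leaving these patients out may itself be selective.

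Whether other treatment is permitted during the study is left to the sponsor.

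**Cost.** The change needs one eligibility line, one case report form item per visit and a short addition to Statistical methods. A few candidates become ineligible or must wait. The sensitivity analysis loses a little power: for an assumed true change of -0.6 mm with SD 1.0 mm, the noncentral t (noncentrality 0.6 × √n) gives 89% at n = 30, 85% at n = 27 and 80% at n = 24.
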